4.10 Overall Survival (OS)

OS will be measured from treatment start date to death or last follow up. After treatment is discontinued for any reason, patients will be followed every 3 months for progression and survival for a maximum of 5 years.

5.0 ADVERSE EVENT REPORTING

5.1 Adverse Events and Laboratory Abnormalities

Toxicity will be graded per CTCAE version 4.03. An AE is any untoward medical occurrence in a patient or clinical investigation subject who has been enrolled in a clinical study and who may have been given an investigational product, regardless of whether or not the event is assessed as related to the study treatment. An AE can therefore be any unfavorable and unintended sign (including an abnormal laboratory finding), symptom, or disease temporally associated with the use of an investigational product, regardless of whether or not the event is assessed as related to the investigational product. Pre-existing medical conditions that worsen during a study should be recorded as AEs. Abnormal laboratory values, electrocardiogram (ECG) findings, or vital signs are to be recorded as AEs if they require clinical intervention or results in changes in study therapy. All untoward events that are thought to be probably/definitely treatment related should be followed until resolution even after study treatment has been discontinued. This requirement includes AEs from unscheduled as well as scheduled visits.

As soon as an investigator becomes aware of an AE that meets the definition of 'serious,' this should be documented to the extent that information is available.

- This report must be submitted by the study site to Karmanos Cancer Institute and Bristol-Myers Squibb within 24 hours via a Medwatch form, even if it is not felt to be drug related.
- Email: [contact] or [contact]
- The investigator agrees to provide supplementary information requested by the PI or designee.

- Pregnancy, although not itself an SAE, should also be reported on a Medwatch form and be followed up to determine outcome, including spontaneous or voluntary termination, details of birth, and the presence or absence of any birth defects or congenital abnormalities.

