A *nonserious adverse event* is an AE not classified as serious.

Nonserious Adverse Event Collection and Reporting

The collection of nonserious AE information should begin at initiation of study drug. All nonserious adverse events (not only those deemed to be treatment-related) should be collected continuously during the treatment period and for a minimum of 100 days following the last dose of study treatment.

Nonserious AEs should be followed to resolution or stabilization, or reported as SAEs if they become serious. Follow-up is also required for nonserious AEs that cause interruption or discontinuation of study drug and for those present at the end of study treatment as appropriate.

Laboratory Test Abnormalities

All laboratory test results captured as part of the study should be recorded following institutional procedures. Test results that constitute SAEs should be documented and reported as such.

The following laboratory abnormalities should be documented and reported appropriately:

- any laboratory test result that is clinically significant or meets the definition of an SAE
- any laboratory abnormality that required the subject to have study drug discontinued or interrupted
- any laboratory abnormality that required the subject to receive specific corrective therapy.

Pregnancy

If, following initiation of the investigational product, it is subsequently discovered that a study subject is pregnant or may have been pregnant at the time of investigational product exposure, including during at least 6 halflives after product administration, the investigational product will be permanently discontinued in an appropriate manner (eg, dose tapering if necessary for subject safety).

The investigator must immediately notify Worldwide Safety @BMS of this event via the Pregnancy Surveillance Form in accordance with SAE reporting procedures.

Follow-up information regarding the course of the pregnancy, including perinatal and neonatal outcome and, where applicable, offspring information must be reported on the Pregnancy Surveillance Form [provided upon request from BMS]

Any pregnancy that occurs in a female partner of a male study participant should be reported to BMS. Information on this pregnancy will be collected on the Pregnancy Surveillance Form.

Overdose

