7.5 Dose Delay Criteria

Because of the potential for clinically meaningful nivolumab-related AEs requiring early recognition and prompt intervention, management algorithms have been developed for suspected AEs of selected categories. [see current Investigator Brochure and Appendix D for citation examples]

Dose delay criteria apply for all therapy related adverse events (regardless of whether or not the event is attributed to nivolumab).

Nivolumab administration should be delayed for the following:

Any Grade ≥ 2 non-skin, drug-related AE, with the following exceptions:

- Grade 2 drug-related fatigue or laboratory abnormalities do not require a treatment delay
- Any Grade 3 skin, drug-related AE

Any Grade 3 drug-related laboratory abnormality, with the following exceptions for lymphopenia, leukopenia, AST, ALT, total bilirubin, or asymptomatic amylase or lipase:

- Grade 3 lymphopenia or leukopenia does not require dose delay.
- If a subject has a baseline AST, ALT, or total bilirubin that is within normal limits, delay dosing for drug-related Grade ≥ 2 toxicity.
- If a subject has baseline AST, ALT, or total bilirubin within the Grade 1 toxicity range, delay dosing for drug-related Grade ≥ 3 toxicity.
- Any Grade ≥ 3 drug-related amylase or lipase abnormality that is not associated with symptoms or clinical manifestations of pancreatitis does not require dose delay. The Investigator should be consulted for such Grade ≥ 3 amylase or lipase abnormalities.

Any AE, laboratory abnormality, or intercurrent illness which, in the judgment of the investigator, warrants delaying the dose of study medication.

Subjects who require delay of nivolumab should be re-evaluated as clinically indicated and resume nivolumab dosing when re-treatment criteria are met.

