7.8 Discontinuation Criteria

Treatment should be permanently discontinued for the following:

- Grade 4 neutropenia lasting > 7 days
- Any Grade 2 drug-related uveitis or eye pain or blurred vision that does not respond to topical therapy and does not improve to Grade 1 severity within the re-treatment period OR requires systemic treatment
- Any Grade 3 non-skin, drug-related adverse event lasting > 7 days, with the following exceptions for drug-related laboratory abnormalities, uveitis, pneumonitis, bronchospasm, hypersensitivity reactions, and infusion reactions, and endocrinopathies:
 - Grade 3 drug-related uveitis, pneumonitis, bronchospasm, hypersensitivity reaction, or infusion reaction of any duration requires discontinuation
 - Grade 3 drug-related endocrinopathies adequately controlled with only physiologic hormone replacement do not require discontinuation
 - Grade 3 drug-related laboratory abnormalities do not require treatment discontinuation except those noted below
 - Grade 3 drug-related thrombocytopenia > 7 days or associated with bleeding requires discontinuation
 - Any drug-related liver function test (LFT) abnormality that meets the following criteria require discontinuation:
 - AST or ALT > 8 x ULN
 - Total bilirubin > 5 x ULN
 - Concurrent AST or ALT > 3 x ULN and total bilirubin > 2 x ULN

- AST or ALT $> 3 \times$ ULN with the appearance of fatigue, nausea, vomiting, right upper quadrant pain or tenderness, fever, rash, and/or eosinophilia ($>5\%$) should lead to treatment discontinuation.
- Any Grade 4 drug-related adverse event or laboratory abnormality, except for the following events which do not require discontinuation:
 - Isolated Grade 4 amylase or lipase abnormalities that are not associated with symptoms or clinical manifestations of pancreatitis and decrease to $<$ Grade 4 within 1 week of onset.
 - Isolated Grade 4 electrolyte imbalances/abnormalities that are not associated with clinical sequelae and are corrected with supplementation/appropriate management within 72 hours of their onset
 - Grade 4 lymphopenia or leucopenia

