8.4 Analysis

8.4.1 For the Primary Objective, the censored PFS distribution will be summarized with the Kaplan-Meier (K-M) survivorship estimate. A graph of the K-M curve for PFS will be generated along with the Hall-Wellner 95% confidence band, and a display of the number of patients at risk at several time points, below the X-axis. Summary statistics (12-month PFS rate, median PFS, etc.) will be calculated from the K-M life table, each one with its respective 95% confidence interval (CI). To test whether the point estimate of the 12-month PFS rate is statistically significantly greater than the assumed historical reference value of 0.50, the point estimate will be compared to the upper critical value of 0.64 obtained from the “One Arm Survival” program mentioned in Section 8.3.

8.4.2 For Secondary Objective (1) toxicity rates will be estimated among the toxicity evaluable patients (defined in Section 4.7). Frequency distributions of each toxicity type by severity grade will be generated. For a given grade(s), the point estimate of the toxicity rate will be computed, along with its 95% (Wilson type) CI.

8.4.3 For Secondary Objective (2), the ORR will be estimated among the response evaluable patients (defined in Section 4.6), and among all patients. Frequency distributions of best response will be generated for each of those sets of patients. The point estimate of the ORR will be computed, along with its 95% (Wilson type) CI.

8.4.4 For Secondary Objectives (3) and (4), summary statistics of MFS and OS will be calculated from their respective K-M life tables in the similar fashion as described in Section 8.4.1 for OS. K-M graphs of the censored MFS and OS distributions will also be generated.

8.4.5 For Secondary Objective (5), the QOL data will be used to test the following hypotheses:

1. Demographics and clinical variables (age, sex, race/ethnicity) will be related to length of time on trial (i.e., days or weeks);
2. Demographic and clinical variables (cancer stage, performance status, number of comorbidities) will be related to: (a) average levels of QOL; and (b) variability in QOL over the course of the trial.

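### Sections 5.1 and 5.5 set different tests for recording laboratory abnormalities and 8.4.2 names no data source, so laboratory toxicity rates may be understated, mainly at Grade 3 and below, and may differ by site

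*Combined protocol and SAP*

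**What the plan says.** **What becomes an AE.** Section 5.1 defines an AE broadly, in relation to the study drug: "An AE can therefore be any unfavorable and unintended sign (including an abnormal laboratory finding), symptom, or disease temporally associated with the use of" (the sentence then names the product). In the same paragraph it adds a sentence specific to laboratory values, ECG findings and vital signs: these "are to be recorded as AEs if they require clinical intervention or results in changes in study therapy".

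**What is documented.** The laboratory part of section 5.5 says: "All laboratory test results captured as part of the study should be recorded following institutional procedures". It then lists what must be documented and reported. The list includes abnormalities that led to interruption, discontinuation or corrective therapy, but it begins with "any laboratory test result that is clinically significant or meets the definition of an SAE". On AEs in general, 5.5 says: "All nonserious adverse events (not only those deemed to be treatment-related) should be collected continuously during the treatment period".

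**What triggers a change in therapy.** Section 7.5 states that "Grade 3 lymphopenia or leukopenia does not require dose delay". It also exempts Grade 2 drug-related laboratory abnormalities from delay, apart from its separate rules for AST, ALT and bilirubin. Section 7.8 exempts Grade 3 drug-related laboratory abnormalities from discontinuation, apart from listed thrombocytopenia and liver criteria. Among the Grade 4 events that do not require discontinuation it lists "Grade 4 lymphopenia or leucopenia".

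**What is tabulated.** Section 8.2.2 refers to Section 5 as a whole for toxicity assessment. Section 8.4.2 promises: "Frequency distributions of each toxicity type by severity grade will be generated", with Wilson 95% intervals, among toxicity-evaluable patients. It names no data source.

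**The concern.** Toxicity of concurrent nivolumab and radiation is the first secondary objective. A rate by grade is useful only if an event of that grade has the same chance of being counted whatever was done about it. Under the 5.1 sentence, the chance of being counted depends on whether someone treated the abnormality or changed therapy, and 7.5 and 7.8 say that for several common laboratory findings no change in therapy is required. For those findings the table would partly measure clinicians' actions.

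The second difficulty is consistency. A coordinating centre and about 2-3 further sites (section 1.5) will read two tests that are not equivalent. A site that works from 5.1 can leave out an event that a site working from 5.5 enters. With about 30 patients, a few such differences change a reported rate visibly. The monitoring report in Appendix E lists Grade 3 to 5 adverse events, so a value never classed as an AE could be absent there as well.

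**Working it through.** There is no figure in the plan to reproduce. The check is a comparison of rules, followed by an illustration of size.

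**Step 1. Follow an untreated case through the rules.** Take a patient with asymptomatic Grade 3 lymphopenia on a pre-dose count, given no treatment for it and dosed on time.
- Section 7.5: no delay required.
- Section 7.8: no discontinuation required.
- Section 5.1, laboratory sentence: neither condition is met, so the sentence does not call for an AE entry.
- Section 5.1, general definition: the finding can be an AE.
- Section 5.5: the result is recorded under institutional procedures. It is documented and reported if judged clinically significant, a term the section does not define. The section does not say that such a result becomes an AE.
- Section 8.4.2: if the source is AE forms, the case may or may not be counted; if the source is laboratory values, it is counted.

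The same path applies to most Grade 2 laboratory abnormalities, and Grade 1 changes that prompt no action also fail the 5.1 test.

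**Step 2. Grade 4.** Section 7.8 removes the requirement to discontinue for Grade 4 lymphopenia or leukopenia. The delay exemption in 7.5 names Grade 3 only. A Grade 4 case that led to a delay would meet the 5.1 test. The gap is therefore clearest at Grade 3 and below.

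**Step 3. Are the values available?** Blood count with differential and chemistry are scheduled at every treatment visit (section 2.3, footnote 1) and within 72 hours before re-dosing (section 4.2). Amylase and lipase are in neither list, although 7.5 and 7.8 refer to them.

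**Step 4. Illustrate the size.** Inputs: n = 30 evaluable patients (section 8.3, where evaluable for PFS and toxicity-evaluable share a definition) and the Wilson interval named in 8.4.2. The true rates of 10%, 20% and 30% are assumptions; the documents give none.

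Wilson 95% interval, with p = x/n and z = 1.96:

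(p + z²/2n ± z√[p(1−p)/n + z²/4n²]) / (1 + z²/n)

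For x = 0 the upper limit reduces to z²/(n + z²) = 3.8415/33.8415 = 11.4%.

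For x = 6: (0.2 + 0.0640 ± 1.96√[0.00533 + 0.00107]) / 1.128 = (0.2640 ± 0.1568)/1.128, which is 9.5% to 37.3%.

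| Scenario | Count | Rate | Wilson 95% CI |
|---|---|---|---|
| Worst case, every case missed | 0/30 | 0% | 0 to 11.4% |
| Assumed true rate 10% | 3/30 | 10% | 3.5 to 25.6% |
| Assumed true rate 20% | 6/30 | 20% | 9.5 to 37.3% |
| Assumed true rate 30% | 9/30 | 30% | 16.7 to 47.9% |

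Partial recording falls in between. If 6 of 30 patients had the event and half were entered (both assumed), the table would show 0.5 × 6 = 3, that is 3/30 in place of 6/30. Omission can only lower the count.

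**The case against.** A reader might infer that laboratory values count as AEs only when acted on, that Grade 3 and 4 lymphopenia and leukopenia are exempt from any action, and that the tables would therefore show none however often these events occur. The documents do not support this.

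- Section 5.1 says if, not only if, and its general definition covers abnormal laboratory findings.
- Section 5.5 adds clinically significant results and asks that all nonserious AEs be collected. Section 8.2.2 points to Section 5 as a whole, and section 2.3 schedules a toxicity assessment at every visit.
- The exemptions are partial: Grade 3 from required delay, and Grade 4 from required discontinuation. Section 7.5 leaves the investigator free to delay for any laboratory abnormality, and neither section rules out treating one.

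The zero row is therefore a worst case. Nor should the intervals be compared as if they were independent samples: both counts would come from the same patients, and 0 to 11.4% fails to overlap only the interval for the assumed 30%, not those for 10% or 20%.

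It can also be said that toxicity is descriptive here, with no test or stopping rule tied to laboratory rates, and that recording laboratory AEs when they are acted on or clinically significant is a recording convention. That limits the weight of the point.

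What remains is that 5.1 and 5.5 apply different tests, that 5.5 does not make a clinically significant result an AE, and that 8.4.2 leaves the source open. The recording of raw results under institutional procedures does not by itself put them in the analysis data, because section 10.4 limits submission to what the CRFs require.

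**Conclusion.** The concern holds as a risk of under-recording and of inconsistent recording between sites, mainly at Grade 3 and below, if the 8.4.2 tables are built from AE forms. Any bias from omitted cases is downward.

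Its size cannot be derived from the documents. It lies between no loss, if sites enter every abnormality under the general AE definition, and the worst-case 0/30. The comparison rates of 10%, 20% and 30% are assumptions, and n = 30 is the planned evaluable number. The documents do not establish that these events would be missing altogether, and they do not support that claim for Grade 4.

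The primary endpoint is unaffected. The change is worth making because it concerns the first secondary objective and rests on blood tests already scheduled.

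**What to change.** 1. In 8.4.2, state that CTCAE 4.03 grades for the scheduled blood count and chemistry are derived from the numeric values in all toxicity-evaluable patients. Report the worst post-baseline grade and the shift from baseline. The shift is needed because section 3.1 admits patients with reduced creatinine clearance and sets no lymphocyte limit, so some abnormalities may precede treatment.
2. Report these laboratory tables separately from investigator-recorded AEs.
3. Give 5.1 and 5.5 a single rule for which laboratory abnormalities are also entered as AEs. If clinical significance stays as the test, define it.

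None of this alters the delay or discontinuation rules.

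**Cost.** One derivation and one set of tables. The CRFs are not among the documents, so it must be confirmed that the numeric values are in the eCRF; if they are not, they must be added and entered. Reported laboratory toxicity rates will look higher. Amylase and lipase are not in the scheduled panel and would not be covered.

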5.2 Local IRB reporting

Reporting is also required per the local IRB reporting procedures for each site.

5.3 Adverse event reporting to BMS

- All treatment related or unrelated Serious Adverse Events (SAEs) that occur following the subject's written consent to participate in the study through 100 days of discontinuation of dosing must be reported to Karmanos Cancer Institute and BMS Worldwide Safety.
- For subjects consented and never treated with study drug, SAEs should be collected for 30 days from the date of consent.
- If the BMS safety address is not included in the protocol document (e.g. multicenter studies where events are reported centrally), the procedure for safety reporting must be reviewed/approved by the BMS Protocol Manager. Procedures for such reporting must be reviewed and approved by BMS prior to study activation.
- The Medwatch/BMS form should be used to report SAEs. If the BMS form cannot be used, another acceptable form (i.e. CIOMS or Medwatch) must be reviewed and approved by BMS. The BMS protocol ID number must be included on whatever form is submitted by the Sponsor/Investigator.
- Following the subject's written consent to participate in the study, all SAEs, whether related or not related to study drug, are collected, including those thought to be associated with protocol-specified procedures. The investigator should report any SAE occurring after these time periods that is believed to be related to study drug or protocol-specified procedure. For drugs with potential for delayed SAEs (e.g., delayed excretion of the parent or active metabolites), a longer follow-up period may be warranted to allow collection of these SAEs, laboratory tests, and other assessments.
- For studies with long-term follow-up periods in which safety data are being reported, include the timing of SAE collection
- In accordance with local regulations, BMS will notify investigators of all reported SAEs that are suspected (related to the investigational product) and unexpected (i.e., not previously described in the IB). In the European Union (EU), an event meeting these criteria is termed a Suspected, Unexpected Serious Adverse Reaction (SUSAR). Investigator notification of these events will be in the form of an expedited safety report (ESR).

- Other important findings which may be reported by the as an ESR include: increased frequency of a clinically significant expected SAE, an SAE considered associated with study procedures that could modify the conduct of the study, lack of efficacy that poses significant hazard to study subjects, clinically significant safety finding from a nonclinical (eg, animal) study, important safety recommendations from a study data monitoring committee, or sponsor decision to end or temporarily halt a clinical study for safety reasons.
- Upon receiving an ESR from BMS, the investigator must review and retain the ESR with the IB. Where required by local regulations or when there is a central IRB/IEC for the study, the sponsor will submit the ESR to the appropriate IRB/IEC. The investigator and IRB/IEC will determine if the informed consent requires revision. The investigator should also comply with the IRB/IEC procedures for reporting any other safety information.
- In addition, suspected serious adverse reactions (whether expected or unexpected) shall be reported by BMS to the relevant competent health authorities in all concerned countries according to local regulations (either as expedited and/or in aggregate reports).

5.4 Serious Adverse Event Collection and Reporting

Following the subject's written consent to participate in the study, all SAEs, whether related or not related to study drug, must be collected, including those thought to be associated with protocol-specified procedures. All SAEs must be collected that occur within 100 days of discontinuation of dosing.

All SAEs must be collected that occur during the screening period. If applicable, SAEs must be collected that relate to any protocol-specified procedure (e.g., a follow-up skin biopsy). The investigator should report any SAE that occurs after these time periods that is believed to be related to study drug or protocol-specified procedure.

SAEs, whether related or not related to study drug, and pregnancies must be reported to Karmanos Cancer Institute and BMS within 24 hours. SAEs must be recorded on Medwatch form; pregnancies also on a Medwatch form.

SAE Email Address: [contact]

SAE [contact]

If only limited information is initially available, follow-up reports are required. (Note: Follow-up SAE reports should include the same investigator term(s) initially reported.)

If an ongoing SAE changes in its intensity or relationship to study drug or if new information becomes available, a follow-up SAE report should be sent within 24 hours to the BMS (or designee) using the same procedure used for transmitting the initial SAE report.

All SAEs should be followed to resolution or stabilization.

The Sponsor/Investigator will ensure that all SAEs in the clinical database are reported to BMS and any applicable health authority during the conduct of the study including periodic reconciliation.

For studies conducted under an Investigator IND in the US include the following timelines or text:

For studies conducted under an Investigator IND in the US, any event that is both serious unexpected and related must be reported to the Food and Drug Administration (FDA) as soon as possible and no later than 7 days (for a death or life-threatening event) or 15 days (for all other SAEs) after the investigator's or institution's initial receipt of the information. BMS will be provided with a simultaneous copy of all adverse events filed with the FDA.

SAEs should be reported on MedWatch Form 3500A, which can be accessed at: <http://www.accessdata.fda.gov/scripts/medwatch/>.

MedWatch SAE forms should be sent to the FDA at:

MEDWATCH
[name]
[name]
Fax: [name] ([name])
<http://www.accessdata.fda.gov/scripts/medwatch/>

All SAEs should simultaneously be faxed or e-mailed to BMS at:

Global Pharmacovigilance & Epidemiology
Bristol-Myers Squibb Company
[contact]
Email: [contact]

- An SAE report should be completed for any event where doubt exists regarding its seriousness.
- For studies with long-term follow-up periods in which safety data are being reported, include the timing of SAE collection in the protocol.
- If the investigator believes that an SAE is not related to study drug, but is potentially related to the conditions of the study (such as withdrawal of previous therapy or a complication of a study procedure), the relationship should be specified in the narrative section of the SAE Report Form.
- If only limited information is initially available, follow-up reports are required. (Note: Follow-up SAE reports should include the same investigator term(s) initially reported.)
- If an ongoing SAE changes in its intensity or relationship to study drug or if new information becomes available, a follow-up SAE report should be sent within 24 hours to BMS using the same procedure used for transmitting the initial SAE report.

All SAEs should be followed to resolution or stabilization. All SAEs should be followed to resolution or stabilization.

